4.1.2 Primary Endpoint 2 – Implant Success

The purpose of primary endpoint 2 is to evaluate the implant success rate of Solia S lead in the LBB area.

The following hypotheses have been defined to evaluate the primary efficacy endpoint:

H₀: The implant success rate of Solia S lead in the LBB area is less than or equal to 80%.

Implant Success Rate \leq 80%

H_a: The implant success rate of Solia S lead in the LBB area is greater than 80%.

Implant Success Rate > 80%

Primary endpoint 2 will be evaluated by performing an exact, binomial test comparing the observed proportion (implant success rate) to the performance goal of 80%. The lower, two-sided 95% confidence bound for the overall implant success rate must be greater than 80% to reject the null hypothesis (H₀), which would demonstrate evidence that the rate of successful Solia S LBBAP implants is significantly higher than 80.0%.

Definition of Implant Success

Implant success is defined as successful placement in the LBB area with a pacing threshold of less than or equal to 2.5 V at 0.4 ms and a mean sensing value of greater than or equal to 2.0 mV in the final lead position. Evaluation of the mean sensing value is not required for patients that are pacing dependent.

For the BIO-CONDUCT study, successful placement in the LBB area is defined as: a) presence of two or more of the criteria listed below as determined and documented by the investigator, with b) at least one of Criterion #1 or #2 being met. (Huang W et al. 2019, Vijayaraman et al. 2021, De Pooter et al. 2020, Wu et al. 2021):

1. Paced QRS morphology that presents with a right bundle branch block (RBBB) pattern
2. Peak LV activation time (stimulus to peak of the R wave in leads V4 to V6) of < 90ms at high and low-output pacing
3. Presence of LBB potentials (LBB-V intervals of 15 to 35ms)
4. Demonstration of output-dependent non-selective LBBAP and selective LBBAP at near threshold outputs

Sample Size Determination for Primary Endpoint 2

Expectations for implant success are based on published findings for LBB area pacing (Table 3).

Table 3: LBB Area Pacing—Published Implant Success Results

Study	Total Subjects (n)	Subjects with successful implant (n)	Success Rate	95% CI – Lower Bound
Su L et al. 2021	632	618	97.8%	96.3%
Padala S et al. 2020	341	305	89.4%	85.7%
Li X et al. 2021	246	235	95.5%	92.1%
Vijayaraman P et al. 2019	100	93	93.0%	86.0%
Wang J et al. 2020	66	61	92.4%	83.1%
De Pooter J et al. 2020	50	44	88.0%	75.8%
Li X et al. 2019	33	30	90.9%	75.7%
Zhang S et al. 2021	33	29	87.9%	72.1%
Huang W et al. 2020	63	61	96.8%	88.5%

It is expected that the Solia S when implanted in the LBB area will have an implant success of 88.0%, which is similar to published rates. The assumed performance (88.0%) and performance goal of 80.0% are compared to the published safety results in Figure 2.

[figure not shown]

Figure 2: Assumed Implant Success Compared to Published Results

The estimated sample size required to evaluate primary endpoint 2 is based on a superiority comparison of overall Solia S leads successfully implanted to 80%. The sample size for primary endpoint 2 was calculated based on the following assumptions.

- Study Design: Non-randomized
- Type I error (alpha): 0.025 (one-sided for superiority)
- Statistical power: 80%
- Performance Goal for Successful Implant Rate: 80%
- Expected Successful Implant Rate: 88%
- Test basis: Exact binomial test
- Attrition Rate: 5%

For primary endpoint 2, a total of 175 evaluable Solia S leads would be required to demonstrate superiority to a successful implant rate of 80%. Assuming a 5% attrition rate, a total of 184 (= 175 / 0.95) patients with a Solia S lead would be required to be enrolled to evaluate primary endpoint 2.

4.1.3 Secondary Endpoint 1: Quality of Life (QOL) Through 12 Months Post-Implant

The purpose of secondary endpoint 1 is to evaluate the improvement in QOL for patients with successful Solia S lead implantation in the LBB area. Specifically, the physical function scale of the SF-36 will be used as it has been shown to be the best all-around measure of physical health (Ware JE Jr. et al. 2000). The QOL scale is standardized such that a higher score indicates better physical health.

The following hypotheses have been defined to evaluate the improvement in quality of life:

H_0 : The improvement in quality of life through 12 months post-implant for subjects with successful Solia S lead implanted in the LBB area is less than or equal to 2.8

$$\text{Improvement in QOL}_{\text{Physical Function Scale}} \leq 2.8$$

H_a : The improvement in quality of life through 12 months post-implant for subjects with successful Solia S lead implanted in the LBB area is greater than 2.8

$$\text{Improvement in QOL}_{\text{Physical Function Scale}} > 2.8$$

Secondary endpoint 1 will be evaluated by performing an exact one-sample t-test comparing the mean improvement in QOL from baseline to 12 months post-implant to the performance goal of 2.8. The lower, two-sided 95% confidence bound for the improvement in QOL must be greater than 2.8 to reject the null hypothesis (H_0), which would demonstrate evidence that the improvement in QOL is significantly higher than 2.8.

For the secondary endpoint 1 analysis, ITT population subjects with evaluable QOL paired baseline and 12-month measurements will be included. Subjects for which a baseline or 12-month physical function QOL score cannot be calculated, either due to missing or incomplete QOL data, will be excluded from the analysis.

Sample Size Determination for Secondary Endpoint 1

Prior studies evaluating the quality of life in elderly patients receiving dual-chamber pacemakers with standard RV pacing have demonstrated modest improvement (ranging from 2.7 to 4; weighted mean of 2.8) in QOL as assessed by the SF-36 physical function scale from baseline (pre-implant) to 12 months post-implant (Fleischmann KE et al. 2006, Yu CM et al. 2014). More recently, Li H et al. (2021), found patients experiencing pacemaker-induced cardiomyopathy that were upgraded from RV pacing to LBB area pacing had a higher score in the physical function scale by 18.2 points at 12 months post-upgrade. At 24 months post-implant, in a crossover study, Kronborg MB et al. 2014 showed a 5-point improvement as measured by the physical function scale comparing His or para-His pacing to RV pacing. However, this improvement was not shown to be statistically significant. Other studies on conduction system pacing have noted improved QOL in patients receiving this therapy (Lustgarten DL et al. 2015, Occhetta E et al. 2006).

Based on this information, it is anticipated that patients with successful LBB area pacing with the Solia S lead will have an improvement in QOL, as measured by the SF-36 Physical Function score, of at least 10 from pre-implant baseline to 12 months post implant. This improvement in the Physical Function Score with LBB area pacing using a Solia S lead is the expected improvement due to receiving a pacemaker system (pre-implant baseline to RV pacing, average improvement in QOL score = 2.8) plus the additional expected benefit due to utilizing LBB area pacing as compared to RV pacing (expected improvement in QOL score = 7.8; combining LBB vs RVp from Li H et al. and Kronborg MB et al, weighted mean = 7.8). For the sample size calculation, an expected improvement in the Physical function Score was rounded to 10.

The estimated sample size required to evaluate secondary endpoint 1 is based on a superiority comparison of the improvement in QOL (physical function scale) to the expected improvement with RV pacing of 2.8 points. The sample size for secondary endpoint 1 was calculated based on the following assumptions.

Assumptions:

- Study Design: Non-randomized
- Type I error (alpha): 0.025 (one-sided for superiority)
- Statistical power: 80%
- Standard deviation: 30
- Performance Goal for QOL_{Physical Function Scale} Improvement: 2.8
- Expected QOL_{Physical Function Scale} Improvement: 10
- Test basis: Exact one-sample t-test

For secondary endpoint 1, 139 evaluable QOL paired baseline and 12-month measurements would be required to demonstrate superiority to an improved QOL of 2.8 based on a standard deviation of 30. The assumed standard deviation for SF-36 Physical Function Scale score is based on findings from multiple sources using SF-36 for RV pacing (Kronborg MB et al. 2014, Li H et al. 2021, Link MS et al. 2004, Yu CM et al. 2014).

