2.2.2 Secondary Endpoints

One powered secondary endpoint and 4 descriptive secondary endpoints are planned.

1. Quality of Life (QOL) from baseline through 12 Months Post-Implant

The purpose of secondary endpoint 1 is to evaluate the improvement in QOL for subjects with the Solia S lead implanted in the left bundle branch (LBB) area. The parameter of interest is the change in the physical function SF-36 (36-Item Short Form Health Survey) QOL scale from pre-implant baseline to 12 months post-implant, which will be calculated as the mean change from baseline for all subjects that complete both the baseline QOL and 12-month QOL questionnaire.

2. SADE-free rate for Solia S LBB lead through 6- and 12-months post-implant

3. Solia S LBB lead pacing threshold at 3-, 6-, and 12-month follow-up visits

4. Solia S LBB lead R-wave sensed amplitude at 3-, 6-, 12-month follow-up visits

5. Solia S LBB lead pacing impedance at 3-, 6-, 12-month follow-up visits

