2.2.4 Other Planned Analyses

Other planned analyses include subgroup analysis (age ≥ 65 years), poolability analysis to assess the primary outcomes across sites and regions (U.S. and outside of U.S.), and analyses to determine differences in outcomes based on sex and race.

3 General Analysis Considerations

The planned analyses described here will be performed when the data required to complete the analysis is available. A pivotal analysis and interim report of primary endpoint 1 and primary endpoint 2 is planned and will support other analysis required for a PMA submission. Analysis of secondary endpoint 1 and subgroup analysis will be performed after all patients have completed the 12-month study visit or exited the study.

For annual progress reports, the results of completed analyses will be provided when available. If the planned analysis time point has not yet been met, progress toward the analysis and current available data will be presented using descriptive statistics within the annual progress report.

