3.2 Analysis Populations

All clinical data will be analyzed based upon the pre-defined analysis populations as outlined in Table 1. Additional analysis population considerations for specific analysis are included within the analysis method details (Section 4).

Table 1: Study Analysis Populations

Analysis Population	Definition
Intent-to-Treat (ITT) – Primary Endpoint 1 (Safety), Secondary Endpoint 2	This ITT population is defined as 
 • all enrolled subjects (subjects with successfully implanted Solia S in the LBB area) and • subjects with an unsuccessful implant attempt of the Solia S in the LBB area who had a qualifying primary safety endpoint event prior to their exit from the study.
Intent-to-Treat (ITT) – Primary Endpoint 2 (Efficacy)	This ITT population is defined as 
 • all enrolled subjects (subjects with successfully implanted Solia S in the LBB area) and • subjects with an unsuccessful implant attempt of the Solia S in the LBB area.
Intent-to-Treat (ITT) – Secondary Endpoint 1 (QOL), Secondary Endpoints 3-5	This ITT population is defined as 
 • all enrolled subjects (subjects with successfully implanted Solia S in the LBB area)

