3.3 Handling of Missing Data

All reasonable methods will be taken to ensure a minimum of missing data, including site monitoring, training, and corrective actions, if required, ongoing review of collected data for accuracy and completeness, and repeated, documented attempts to contact subjects with missing study visits. Any reasons for missing data or withdrawal from the study will be documented when possible.

If warranted, the impact of missing data on conclusions about the primary study endpoints will be examined in sensitivity analyses, which may include multiple imputation methods.

For secondary endpoint 1, missing QOL data at either the baseline or 12-month follow-up visit affects the number of subjects that can be included in the analysis. It is anticipated that subjects may either forget or choose not to answer one or more of the questions in the QOL. In some cases, subjects may also provide two answers for one or more of the questions. There is no appropriate method to correct these QOL questionnaires after the subject completes the visit.

If needed to ensure sufficient subjects to analyze secondary endpoint 1, an analysis using the last observation carried forward principle and/or average replacement for missing QOL answers or QOL questions with multiple answers may be performed. Additionally, last observation carried forward may be used in cases for which the QOL questionnaire is not completed at the 12-month visit. If there are more than 10% of subjects with missing answers, an assessment of the cause for the missing answers will be performed. If the assessment is such that a random cause can be assumed, then a multiple imputation technique that accounts for variability in imputation will be utilized. Additionally, where missing data are imputed, sensitivity analyses will be completed.

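### Secondary endpoint 1 (QOL): the SAP tests complete pairs in 4.1.3, provides LOCF and conditional multiple imputation in 3.3, and does not say which result is compared with 2.8

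*SAP*

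**What the plan says.** SAP 2.2.2 defines the parameter as the "mean change from baseline for all subjects that complete both the baseline QOL and 12-month QOL questionnaire". SAP 4.1.3 repeats the restriction to evaluable pairs and states: "Subjects for which a baseline or 12-month physical function QOL score cannot be calculated, either due to missing or incomplete QOL data, will be excluded". Success requires the lower limit of the two-sided 95% interval to exceed 2.8. SAP 3.5 allows the test only after both primary endpoints succeed. SAP 3.2, introducing Table 1, sends further population rules for individual analyses to Section 4.

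SAP 3.3 adds three provisions for the same endpoint:

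- A conditional option: "If needed to ensure sufficient subjects to analyze secondary endpoint 1, an analysis using the last observation carried forward principle and/or average replacement" may be performed for missing or doubly answered items.
- A second option: "Additionally, last observation carried forward may be used in cases for which the QOL questionnaire is not completed at the 12-month visit".
- A trigger: "If there are more than 10% of subjects with missing answers, an assessment of the cause for the missing answers will be performed". If a random cause can then be assumed, "then a multiple imputation technique that accounts for variability in imputation will be utilized". Sensitivity analyses are to follow wherever data are imputed, but they are not named.

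On timing, SAP Section 3 says: "Analysis of secondary endpoint 1 and subgroup analysis will be performed after all patients have completed the 12-month study visit or exited the study".

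**The concern.** One section drops subjects without a calculable 12-month score. Another allows that score to be carried forward, or requires imputation under a stated condition. Section 4.1.3 does not refer to 3.3, and no sentence ranks the results or labels any of them supportive. Section 3.3 also gives no method for the case where the cause of missingness is judged not random, which is the case that matters most.

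The analysis is run once the amount of missing data is known. Because each route is already in the SAP, choosing among them would arguably not be a change that Section 5 requires to be documented.

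There is a second problem whichever route is taken. In a single-arm comparison with a fixed goal, no control arm offsets selective dropout. If subjects who do worse return fewer questionnaires, the completers' mean is too high. LOCF can err in either direction, depending on whether the carried score lies above or below what the 12-month score would have been.

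**Working it through.** **1. The plan's own figure.** Inputs from SAP 4.1.3: one-sided alpha 0.025, SD 30, goal 2.8, expected improvement 10, one-sample t-test. Difference = 10 − 2.8 = 7.2. Power = 1 − F(t(0.975, n−1)), where F is the noncentral t distribution with n−1 degrees of freedom and noncentrality 7.2·√n/30. At n = 138 this is 79.9%; at n = 139 it is 80.2%. The 139 pairs are reproduced.

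**2. When the provisions can apply together.** I take sufficient subjects to mean 139 pairs. The number of implanted subjects is an assumption:

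- 154 (= 175 × 0.88): pairs fall below 139 above 1 − 139/154 = 9.7% missing.
- 162 (= 184 × 0.88): above 1 − 139/162 = 14.2%.
- 184 (the enrolment figure in SAP 4.1.2): above 1 − 139/184 = 24.5%.
- 260 (the maximum in SAP 2.2): above 1 − 139/260 = 46.5%.

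With 162 subjects and 10% to 14% missing, the paired test has its planned size and the imputation rule can also be in force. At SD 30, the mean needed to pass is 7.83 with 139 pairs and 7.45 with 162 completed subjects, so the choice can change the result.

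**3. How often completers and imputation disagree.** Simulation assumptions, not in the documents: 15% of 12-month scores missing completely at random, true improvement 10, SD 30, equal 6- and 12-month means, whole missing scores imputed by regression on the 6-month change, 20 imputations, 10,000 runs per cell.

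| Implanted | Correlation 0.3 | 0.6 | 0.8 |
|---|---|---|---|
| 154 | 3.7% | 6.3% | 8.1% |
| 184 | 3.1% | 4.5% | 6.1% |
| 260 | 1.3% | 2.1% | 3.0% |

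Separate simulations of the 154-subject cells gave 2.6% at correlation 0.3, about 6% at 0.6 and 7.7% at 0.8. Those figures are read as about 3% to 8% at 154, and about 2% at 260 with correlation 0.6.

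Under the null (154 subjects, 15% missing, correlation 0.6), taking the better of completers and imputation gives a one-sided error of 3.0% against 2.5%.

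**4. Bias of the completer test.** The completers' mean is shifted by (missing fraction) × (gap between observed and missing subjects). At 12% missing and an assumed gap of 10 points, the shift is 0.12 × 10 = 1.2. At about 139 pairs the noncentral t gives a one-sided error of 6.8%. A gap of 5 points gives a shift of 0.6 and 4.2%.

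Simulation with 154 subjects and 12% missing, with dropout depending on the 6-month score, gave about 7% for completers, 1.4% for LOCF and 2.9% for imputation in one illustration. Varying the strength of dependence (log-odds of being missing per SD of 6-month score, correlation 0.6) gives:

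| Log-odds per SD | Gap (points) | Completers | LOCF | Imputation |
|---|---|---|---|---|
| 0.25 | 4.5 | 3.7% | 1.8% | 2.4% |
| 0.5 | 8.8 | 5.9% | 1.3% | 2.5% |
| 0.8 | 13.3 | 8.8% | 0.9% | 2.4% |
| 1.0 | 16.2 | 11.2% | 0.8% | 2.6% |

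LOCF is conservative here, but not in general. With 154 subjects and 10% missing, a carried mean 5 points below or above the true 12-month mean gives about 1.5% or 3.8%.

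**The case against.** **Section 4.1.3 is the specific section and governs.** This is a fair default reading, and the pointer in 3.2 helps it. But that pointer concerns populations, not imputed against observed results, and 3.3 is itself written for this endpoint. Its call for sensitivity analyses after imputation suggests that the imputed result is not itself the sensitivity analysis.

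**Imputation need not contradict the exclusion.** A reader might infer that 3.3 and 4.1.3 flatly contradict each other once missingness passes 10%. The documents do not support that. Passing 10% triggers an assessment of cause; imputation follows only if a random cause can be assumed. Missing answers may also mean single items, since a wholly missing questionnaire has its own LOCF sentence. On that reading, imputed items make the score calculable and the two sections agree. This stands, and it is why the point is an unresolved ambiguity and a missing ranking. It also means that step 3, which imputes whole scores, shows one reading of 3.3.

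**LOCF is optional.** A reader might infer a free choice among three results. The first LOCF clause opens only if subjects are insufficient, which step 2 shows is often not so. Only the second LOCF sentence lacks that condition, and whether it inherits it is unclear. I therefore do not rest the size of the problem on LOCF.

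**The protocol may settle it.** Protocol Appendix A says statistical analyses for this endpoint were added, but that section is not in the supplied text. This limits the point to the SAP.

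**Conclusion.** The point holds for the SAP as written. It tests complete pairs, provides LOCF and conditional imputation for the same endpoint, and leaves open which result is compared with 2.8, what counts as missing answers, and what is done if the cause is not random. That rests on the text alone.

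The size rests on assumptions. Disagreement between completers and imputation is modest and shrinks with sample size, to about 1% in the mildest cell of the grid. The larger risk is completer bias under selective dropout: about 7% one-sided error in the main illustration, and about 4% to 11% over the strengths of dependence tried. The documents give no basis for choosing among those strengths.

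A reader might also infer that study success or the sample size is in doubt. Neither is: the endpoint is tested only after both primaries succeed, and 139 pairs gives 80.2% power.

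**What to change.** In 4.1.3, name one deciding analysis for all successfully implanted subjects with a baseline score. It can be a mixed model for repeated measures, or multiple imputation (already named in 3.3), using the 3-, 6- and 12-month physical function scores and testing the 12-month mean change against 2.8. State how deaths before 12 months are handled.

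In 3.3, remove LOCF as a route to the deciding result, and say whether missing answers covers a whole questionnaire. Align 2.2.2 and 3.3 with 4.1.3. Keep the paired t-test as a sensitivity analysis and add a delta-adjusted one, because neither model removes bias from dropout that depends on the unseen 12-month score.

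The minimum is one sentence in 4.1.3 naming the deciding analysis and labelling the rest as sensitivity analyses. That settles the ranking but not the completer bias.

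The cost is SAP wording and a standard model. Protocol Appendix A shows that QOL is already collected at 3 and 6 months. The downside is that a missing-at-random assumption must be stated. The change should be made before the 12-month data are analysed.

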4.1.4 Secondary Endpoint 2: SADE-Free rate through 6 Months and 12 Months Post-Implant

There are no formal hypotheses for secondary endpoint 2. The SADE-free rate at each timepoint will be calculated as the number of subjects without one or more Solia S LBB lead adverse event divided by the total number of study subjects successfully enrolled and subjects undergoing an unsuccessful implant attempt who have a qualifying Solia S LBB lead complication in percent. A Kaplan-Meier survival analysis (time-to-event) for the will also be performed for each timepoint.

For the secondary endpoint 2 analysis at 6 months, ITT population subjects who have sufficient follow-up data (at least 152 days of follow-up, corresponding to the earliest potential in-window 6-month visit) or experienced a Solia S LBB lead adverse event will be included. Subjects without a Solia S LBB lead adverse event who drop out prior to day 152 will be excluded from the analysis.

For the secondary endpoint 2 analysis at 12 months, ITT population subjects who have sufficient follow-up data (at least 335 days of follow-up, corresponding to the earliest potential in-window 12-month visit) or experienced a Solia S LBB lead adverse event will be included. Subjects without a Solia S LBB lead adverse event who drop out prior to day 335 will be excluded from the analysis.

